4.3.4 Main and supportive between-group analyses of primary and secondary endpoints

Results from main analyses (based on ITT analysis set) will be considered definitive, and the purpose of supportive analyses (based on PP analysis set) is to demonstrate robustness of results from main analyses with different statistical models and in different subject populations. In the event that results from main and supportive analyses differ substantially further exploratory work will be carried out to explain the differences.

Primary Endpoint

The main analysis which gives a between-group assessment will be carried out using the mixed effects model as previously defined on subjects in the ITT analysis set population using maxCIMT data for all carotid artery sites.

A Supportive analysis will also be carried out in a similar way using only subjects in the PP population.

Secondary Endpoints

- MeanMax CCA CIMT

The main and supportive analyses will be as for the main and supportive analyses of the primary endpoint but using maxCIMT data only for sites in the CCA.

- MeanMax Bulb CIMT

The main and supportive analyses will be as for the main and supportive analyses of the primary endpoint but using maxCIMT data only for sites in the carotid artery bulb.

- MeanMax ICA CIMT

The main and supportive analyses will be as for the main and supportive analyses of the primary endpoint but using maxCIMT data only for sites in the ICA.

- MeanMean CCA CIMT

The main and supportive analyses will be as for the main and supportive analyses of the primary endpoint but using meanCIMT values measured in the CCA.

- Percentage change from baseline to final visit in LDL-C (converted values, see section 4.1), total cholesterol, HDL-C, TG, non-HDL-C, ApoB, ApoA-I, non-HDL-C/HDL-C, and ApoB/ApoA-I.

See section 4.3.5 for details.

4.3.5 Laboratory data

Analyses of percentage change from baseline in lipids and lipoproteins will be carried out for the ITT population using ANCOVA with terms for treatment and baseline value as a covariate in the model. For LDL-C, this will be analysed for both sets of LDL-C values (collected and converted) described in section 4.1. However, the converted values will be considered as the secondary endpoint while the collected values will be used for supportive analysis.

The assumptions of normality and homogeneity of variance will be explored using probability and residual plots. If assumptions are found to be violated, rank ANCOVA approach (Quade 1967) will be used.

4.3.6 Other analyses

For each subject in the ITT analysis set (with at least baseline and one post-baseline scan), the slope of the regression line fitted to the profiles of CIMT values for all 12 carotid artery sites will be estimated in mm/year using a fixed effects model with terms for intercept, site, and time applied to each subject's data. The estimate for slope will be determined from the coefficient of time. A positive slope will indicate progression and a negative slope will indicate regression.

The number and percent of subjects with regression will be summarized for each treatment group.

Summaries of MeanMax CIMT, MeanMax CCA CIMT, MeanMax Bulb CIMT, MeanMax ICA CIMT and MeanMean CCA CIMT (mm) by cohort of assessments completed and visit will be provided. Cohorts of assessments will be Completer - 2 years, non-completer but completed up to 18 months, non-completer but completed up to 12 months, non-completer but completed up to 6 months.

The following outputs will be included to assess quality control of scanning and reading of results.

- Summary of number of carotid artery sites measured per scan by visit
- Distribution of number of carotid artery sites measured per scan at each visit
- Number (%) of subjects read by reader
- Number of measurements obtained at each carotid artery site and percentage out of maximum possible

4.3.7 Subgroup analyses

The effects of rosuvastatin in following subgroups of subjects will be evaluated,

1. Age: < 65 and ≥ 65 years
2. Sex
3. BMI: < 28 vs ≥ 28 kg/m²
4. China Adult Dyslipidemia Management Guidelines ICVD risk categories (see 4.2.2 for definitions)
5. History of hypertension (Yes/No)
6. Baseline LDL-C: below and above or equal to the mean
7. Baseline TC: below and above or equal to the mean
8. Baseline HDL-C: below and above or equal to the mean
9. Baseline TG: above and below the mean (If TG are not normally distributed, groupings above and below the median value will be considered).
10. Baseline non-HDL-C: below and above or equal to the mean
11. Baseline non-HDL-C/HDL-C: below and above or equal to the mean
12. Baseline ApoB: below and above or equal to the mean
13. Baseline ApoA-I: below and above or equal to the mean
14. Baseline ApoB/ApoA-I: below and above or equal to the mean
15. Smoking: never, current/former

The treatment-by-subgroup interaction will be examined by adding the subgroup variable and the interaction term of treatment-by-subgroup as covariates to multilevel, repeated measures, linear mixed effects model as described for the primary analysis (section 4.3). Similar output will be presented for each subgroup as for the primary analysis. When the subgroups are also stratification factors, the eCRF values will be used rather than the values from IxRS used for randomization.

For smoking subgroup, if there is any category with less than 10% of the population in a review prior to unblinding the study, the subgroup may be re-categorized or eliminated before unblinding.

These analyses will use the ITT analysis set.

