#### **Study site(s) and number of subjects planned**

Approximately 506 Chinese subjects will be randomized to study treatment. The study will be conducted across approximately 30 sites in China.

543 Chinese subjects were randomized into study when the recruitment was completed, these randomized patients were from 25 sites in China.

---

Study period		Phase of development
Estimated date of first subject enrolled	3Q 2015	Phase 3
Estimated date of last subject completed	1Q 2019	Phase 3

---

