CRESTOR™ (rosuvastatin) is effective at lowering low-density lipoprotein cholesterol (LDL-C) concentrations. In addition, rosuvastatin, like other statins, has favorable effects on other components of the lipid and lipoprotein profile, such as raising high-density lipoprotein cholesterol (HDL-C) and reducing levels of total cholesterol and triglycerides. The principal evidence supporting the anti-atherosclerotic effects of rosuvastatin is based on the findings of METEOR, the pivotal Phase 3 registration study that evaluated the effects of 2-year treatment with rosuvastatin 40 mg on the natural history of atherosclerosis of the carotid arteries ([Crouse et al 2007](#)). The study enrolled 984 patients with hypercholesterolemia who were randomized in a 5:2 ratio to active treatment or placebo (702 rosuvastatin, 282 placebo). Patients were at low risk (defined as 10-year Framingham Risk Index <10%) for CHD according to National Cholesterol Education Panel (NCEP) Adult Treatment Panel (ATP) III guidelines published in 2001 ([NCEP 2001](#)), and they were required to have evidence of subclinical atherosclerosis as assessed by CIMT. Over the 2-year course of the study, rosuvastatin significantly slowed the progression of atherosclerotic disease as compared to placebo. For the primary endpoint, there was a highly significant difference in the change in maximum CIMT across the 12 carotid sites relative to placebo (-0.0145 mm/year; 95% confidence interval for difference -0.0196, -0.0093;  $p < 0.0001$ ). Rosuvastatin also delayed the progression of atherosclerotic disease as evidenced by a negative rate of change across the 12 carotid sites over the 2-year study period (-0.0014 mm/year). This delay in disease progression among the rosuvastatin-treated patients over the 2-year course of the study is particularly noteworthy when viewed in the context of the observed placebo rate of progression of +0.0131 mm/year (95% confidence interval 0.0087, 0.0174;  $p < 0.0001$ ).

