#### **8.5.1 Analysis of the primary efficacy variable**

A linear mixed-effects model will be used for the primary analysis to assess the difference in the annualized rate of change in the CIMT measurements across 12 carotid artery sites between rosuvastatin 20 mg and placebo treatment over 104 weeks.

For the primary efficacy analysis, the dependent variable is the maximum CIMT measurement from 3 interrogation angles at each of the 12 carotid artery sites at each timepoint of CIMT measurement during the 104-week study period. The model includes fixed effects for treatment group, time, time by treatment interaction, ICVD risk stratification (<5%/5% to 10%), age, sex, centre and scan reader, and random effects for the intercept and slope at the individual subject level and carotid artery site within subject. Ultrasound machine will be included as a fixed effect as well if different types of machines are deployed across sites. For time of CIMT measurement, the 2 pre-randomization visits and the final 2 visits at the end-of-study will be treated as separate time points. Details will be defined in the Statistical Analysis Plan. Time, as a continuous variable, is the interval from the date of randomization to the date of CIMT measurement. Differences in annualized change between rosuvastatin and placebo will be evaluated by testing the time-by-treatment interaction term.

In the analysis, let  $\beta_1$  and  $\beta_2$  represent respectively the coefficient parameters for time and time by treatment interaction in the mixed effect model. The annualized rate of change (slope) in MeanMax CIMT in placebo will be estimated by the coefficient parameter  $\beta_1$ , the annualized rate of change (slope) in MeanMax CIMT in rosuvastatin will be estimated by  $\beta_1 + \beta_2$ , and the difference of annualized rate (slope) of change between 2 groups will be estimated by  $\beta_2$ . Then, the null and the alternative primary hypothesis can be expressed as  $H_0: \beta_2 = 0$  vs.  $H_a: \beta_2 \neq 0$  at a significance level of 0.05 two-sided.

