4.3.1 Estimates of effects and tests of statistical significance for trial objectives

Between-group comparisons

In the analysis, let β_1 and β_2 represent respectively the coefficient parameters for time and time by treatment interaction in the mixed effects model. The dependent variable is maximum CIMT.

The annualized rate of change (slope) in MeanMax CIMT in placebo will be estimated by the coefficient parameter β_1 , the annualized rate of change (slope) in MeanMax CIMT in the rosuvastatin group will be estimated by $\beta_1 + \beta_2$, and the difference of annualized rate (slope) of change between 2 groups will be estimated by β_2 . Then, the null and the alternative primary hypotheses can be expressed as

$H_0: \beta_2=0$ vs. $H_a: \beta_2 \neq 0$ at a significance level of $\alpha=0.05$.

In other words, the change in MeanMax CIMT from time zero, measured in mm per year, can be estimated from the model as β_1 (Time) for the placebo group and β_1 (Time) + β_2 (Time x Treatment) for the rosuvastatin group. The estimate of the absolute difference in mm in MeanMax CIMT at 2 years between the treatment groups is β_3 (Treatment) + $2 \beta_2$ (Time x Treatment) and change from baseline at 2 years is $2 \beta_2$ (Time x Treatment).

The treatment effect is based on the Time x Treatment term and represents the difference in slopes in mm/year. The between-group test of statistical significance is the p-value associated with this term in the model.

Further details of the analyses and model are given in the following sections.

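### SAP 4.3.7 tests effect modification by nine baseline lipid measures only after cutting each in two; if modification is roughly linear, this gives up about 25–43% of the information.

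*SAP*

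**What the plan says.** SAP 4.3.7 names fifteen subgroup factors. Items 6–14 are laboratory values: LDL-C, total cholesterol, HDL-C, TG, non-HDL-C, non-HDL-C/HDL-C, ApoB, ApoA-I and ApoB/ApoA-I. The LDL-C entry reads "Baseline LDL-C: below and above or equal to the mean", and seven others use the same rule. The TG entry has a fallback: "Baseline TG: above and below the mean (If TG are not normally distributed, groupings above and below the median value will be considered".

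On the test, the section says: "The treatment-by-subgroup interaction will be examined by adding the subgroup variable and the interaction term of treatment-by-subgroup as covariates". These terms go into the primary mixed model, and output like that of the primary analysis is to be shown for each subgroup. No significance level, power or decision rule is given for the interactions. SAP Appendix C gives no code for them.

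The effect being modified is a slope difference. SAP 4.3.1 says: "The treatment effect is based on the Time x Treatment term and represents the difference in slopes in mm/year".

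The only continuous display involving lipids is the loess plot in SAP 4.3.8. It uses percent change in LDL-C and on-treatment LDL-C, not baseline values, and that section is restricted to the rosuvastatin arm. It cannot show whether the treatment effect varies with baseline lipid level.

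**The concern.** These nine analyses ask whether the effect on carotid intima-media thickness (CIMT) depends on baseline lipid level. Cutting a measured value at the mean treats subjects just either side of the cut as opposites and everyone within a half as alike. If the true relation is a gradient, the two-level test sees it less clearly than the data allow. Interaction tests are weak to begin with, and a further-weakened one makes a null result even less informative.

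The cut also has no stated clinical basis. Other parts of the plan use fixed external values: BMI 28 kg/m² in the same list, and on-treatment LDL-C of 70 and 100 mg/dL in SAP 4.3.8. Protocol Appendix F counts HDL-C below 40 mg/dL as a risk factor, yet the HDL-C subgroup is split at whatever the trial mean proves to be. Such a cut does not carry over to another trial.

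**Working it through.** **No plan figure to reproduce.** The documents state no power or information figure for any subgroup interaction, and the sample-size assumptions are redacted. What follows is a calculation under stated assumptions.

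**Inputs from the documents**
- METEOR, the earlier pivotal trial (Protocol 1.1): difference −0.0145 mm/year, "95% confidence interval for difference -0.0196, -0.0093", with 702 and 282 subjects.
- This trial (Protocol synopsis): "543 Chinese subjects were randomized into study when the recruitment was completed"; allocation 1:1 (Protocol 3.3).
- Test level: the primary test is "at a significance level of 0.05 two-sided". The same level is assumed for the interactions.

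**Assumptions not in the documents**
- The treatment effect changes linearly with the modifier.
- Modifier shape: uniform, normal, or lognormal with log-SD 0.5.
- Slope variability as in METEOR, and no dropout.
- The test is on the slope difference, that is, treatment-by-time-by-modifier.

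**Step 1. Information lost.** With a linear gradient, the relative efficiency of the two-level factor is r², where r is the correlation between the measured value and its split at the mean.

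| Shape | r | r² | Information lost |
|---|---|---|---|
| Uniform | 0.866 | 0.750 | 25% |
| Normal | 0.798 | 0.637 (= 2/π) | 36% |
| Lognormal, log-SD 0.5 | 0.756 | 0.571 | 43% |

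Assumed LDL-C shapes truncated at the entry limits lose 27–30%, or 34–35% with 10% visit-to-visit noise added. For an assumed lognormal TG (log-SD 0.5, below 500 mg/dL) with a gradient linear in TG itself, the loss is 40% at the mean and 45% at the median. If the gradient is linear in log TG and log TG is normal, a median cut loses 36%.

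**Step 2. Cost from 80% power.** At 80% power z = 1.96 + 0.84 = 2.80. After the split z becomes 2.80 × r, and power ≈ Φ(2.80r − 1.96).
- Uniform: 2.80 × 0.866 = 2.43, power 68%, loss 12 points.
- Normal: 2.80 × 0.798 = 2.24, power 61%, loss 19 points.
- Lognormal: 2.80 × 0.756 = 2.12, power 56%, loss 24 points.

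Simulation of a linear interaction on subject slopes (543 subjects, 4,000 runs per case) gave, for measured value against mean split: uniform 80.6% against 68.2%; normal 80.7% against 60.9%; lognormal with coefficient of variation (CV) 0.5, 79.4% against 56.3%.

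**Step 3. Translation to this trial**
- METEOR SE = (0.0196 − 0.0093)/(2 × 1.96) = 0.00263 mm/year.
- Scaling factor = √[(2/271.5)/(1/702 + 1/282)] = 1.217, so SE ≈ 0.0032 mm/year at 543 subjects, 1:1. With 1:1 allocation this is also the SE of the interaction per SD of the modifier.
- Gradient of half the METEOR effect per SD: 0.00725/0.0032 = 2.27, power 62% on the measured value. After the split z is 1.96, 1.81 or 1.71, giving 50%, 44% or 40% (uniform, normal, lognormal), a loss of 12, 18 or 22 points.
- Gradient of a quarter of the METEOR effect per SD: z = 1.13, power about 21% on the measured value. After the split it is about 17%, 15% or 14%, a loss of 4–7 points.

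**Step 4. When the assumption fails.** If modification is a step at the mean, the order reverses. For a normal modifier, power is 59.9% on the measured value and 80.1% on the split.

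**The case against.** **The losses are conditional.** A reader might infer that the plan simply throws away 25–43% of its information. The documents do not support that. They give no baseline lipid distribution and say nothing about the form of any modification, and under a step at the mean the split is the better test. This objection stands, and the figures should be quoted only with their conditions.

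**Large losses need steep gradients.** With an average effect of 0.0145 mm/year, half of it per SD means no effect at 2 SD on one side and double the effect at 2 SD on the other (0.0145 ± 2 × 0.00725). Nothing in the documents points to that. At a quarter per SD both tests are weak, and a null result would not show consistency under either. This also stands: the change improves the test but does not make it adequate.

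**The power figures presume a term the SAP does not state.** Read literally, 4.3.7 adds treatment-by-subgroup without time, which compares CIMT level rather than slope. In a small illustrative simulation (70 runs; assumed slope SD 0.03 mm/year, scan error SD 0.05 mm, subgroup difference in slope effect 0.0145 mm/year), the literal term rejected in about 6% of runs and the three-way term in about 61%. That is a separate and larger problem in the same paragraph. The loss from dichotomising would remain after correcting it, but the figures in Steps 2 and 3 apply only once it is corrected.

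**The cut is not a source of bias.** It is tempting to read a cut at the trial's own mean as open to tuning. It is a prespecified rule on pre-treatment values, and Protocol 8.1 has SAP amendments finished before unblinding. It does not inflate the type I error.

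**Binary subgroups are a legitimate descriptive choice.** This is true for display. It does not explain why the test should use the same two levels.

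**Conclusion.** The point holds as a cheap improvement. SAP 4.3.7 dichotomises nine continuous baseline measures (eight at the mean; TG at the mean or possibly the median) and examines the interaction only on the two-level factor. If modification is roughly linear and the distributions lie between uniform and moderately right-skewed, about 25–43% of the information is lost, or about 12–24 points from 80% power. The loss falls to 4–7 points for a weak gradient and turns into a gain if modification is a step at the mean. The trial-specific figures also assume METEOR's slope variability, no dropout and a correctly specified slope interaction.

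Two stronger inferences should not be drawn. The primary and secondary conclusions do not depend on these analyses. Nor do the documents say that a non-significant interaction will be reported as consistency of effect; that is a risk of interpretation, not a stated rule.

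**What to change.** In SAP 4.3.7, for items 6–14:

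1. Base the interaction test on the baseline value as a centred continuous covariate (log scale for TG).
2. Fit it as a treatment-by-time-by-modifier term with all lower-order terms (modifier, treatment-by-modifier, time-by-modifier), so that it tests modification of the slope difference.
3. Keep the below/above split only to display slope estimates within subgroups.

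**Cost:** SAP wording and a few added model terms per factor; no new data. The downside is that the test assumes an approximately linear gradient and would lose power against a step. The retained split display helps a reader check this, though two groups give only a coarse check.

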#### **8.5.5 Subgroup analysis**

Subgroup analysis of the primary efficacy measurement will be specified in detail in Statistical Analysis Plan.

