Appendix C SAS codes for statistical models used in the efficacy analysis.

Multi-level linear mixed effects model for primary efficacy analysis:

```
PROC MIXED;
CLASS TRT SITE SUBJID ICVD SEX READER CENTRE;
MODEL RESPONSE = TRT TIME TRT*TIME ICVD SITE CENTRE AGE SEX READER
/ SOLUTION DDFM = KR CL COVB;
RANDOM INTERCEPT TIME /SUB = SUBJID TYPE = UN;
RUN;
```

Note: The maxCIMT value for each site will be the dependent variable (RESPONSE) in the mixed effects model. Time is a continuous variable per the protocol and will be the interval in years from date of randomization to date of the CIMT measurement. The fixed effect Time in the MODEL statement is not declared as a class variable; thus it models a linear trend in time. We want to see the change in slope over time for the difference between rosuvastatin and placebo across all sites.

The TYPE=UN option in the RANDOM statement specifies an unstructured covariance matrix for the random intercept and slope effects at the individual subject level.

[figure not shown]
ANCOVA analyses for the laboratory efficacy endpoints:

[figure not shown]
```
PROC GLM;  
CLASS TRT;  
MODEL PER_CHG = TRT BASE /CLPARM;  
LSMEANS TRT / STDERR PDIFF CL;  
ESTIMATE 'ROSUVASTATIN 20 MG VS PLACEBO' TRT 1 -1/CL;  
RUN;
```

PER_CHG = Percentage change from baseline
TRT = Randomized treatment
BASE = Baseline value

[figure not shown]

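### The subgroup interaction in SAP 4.3.7 is treatment-by-subgroup (a CIMT level, mm), not time-by-treatment-by-subgroup (a slope, mm/year), so it does not test whether slowing of progression differs between subgroups

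*SAP*

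**What the plan says.** SAP 4.3.1 is explicit about the estimand: "The treatment effect is based on the Time x Treatment term and represents the difference in slopes in mm/year". It treats the Treatment coefficient as a separate quantity. "The estimate of the absolute difference in mm in MeanMax CIMT at 2 years between the treatment groups is" β3 plus 2β2, so β3 is a level difference in mm and β2 is the slope difference.

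The primary model in SAP Appendix C is "MODEL RESPONSE = TRT TIME TRT*TIME ICVD SITE CENTRE AGE SEX READER", with a random intercept and slope per subject.

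For subgroups, SAP 4.3.7 prescribes: "The treatment-by-subgroup interaction will be examined by adding the subgroup variable and the interaction term of treatment-by-subgroup as covariates". The model that receives these terms is the primary one. The section lists 15 factors and adds: "Similar output will be presented for each subgroup as for the primary analysis". Appendix C contains no subgroup code. Protocol 8.5.5 gives no method and defers: "Subgroup analysis of the primary efficacy measurement will be specified in detail in Statistical Analysis Plan". Neither document names a time-by-subgroup or a time-by-treatment-by-subgroup term.

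**The concern.** When the treatment effect is itself an interaction with time, effect modification is a three-way interaction. A two-way treatment-by-subgroup term asks something else: whether the arms differ in CIMT level by a different amount in the two subgroups, averaged over the profile and anchored at time zero. Randomisation makes that difference zero at time zero, apart from chance imbalance.

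The stated purpose of 4.3.7 is to evaluate the effects of rosuvastatin within subgroups. A programmer who follows the text would produce 15 interaction p-values that do not bear directly on that purpose. A genuine difference in slowing of progression would usually go unseen, and one that was flagged could point the wrong way. A reader could also take non-significant p-values as evidence of a consistent effect when consistency had been imposed by the model.

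**Working it through.** **1. What the model as written can express.** Let SUB be 0 or 1 and t be years from randomisation.

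- As written: mean = β0 + β3·TRT + β1·t + β2·TRT·t + γ·SUB + δ·TRT·SUB (other covariates omitted). The arm difference at time t is β3 + δ·SUB + β2·t. Its rate of change is β2 in both subgroups, and δ is a shift in mm.
- With TIME×SUB and TRT×TIME×SUB (coefficient θ) added, the arm difference is β3 + δ·SUB + (β2 + θ·SUB)·t. Its rate of change is β2 when SUB = 0 and β2 + θ when SUB = 1. The heterogeneity question is θ = 0.

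This part needs no numerical assumption.

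**2. Inputs for the size.** The plan gives no figure to reproduce. Protocol 1.1 reports METEOR: a slope difference of -0.0145 mm/year, with "95% confidence interval for difference -0.0196, -0.0093" and arms of 702 and 282.

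- SE = (0.0196 - 0.0093)/3.92 = 0.00263.
- Effective per-subject slope SD = 0.00263/√(1/702 + 1/282) = 0.0373, which already includes measurement error.

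Assumed: N = 506 in four cells of 126.5; scans at weeks -4, -2, 26, 52, 78, 102 and 104; no dropout; treatment effect only after time zero; analysis of the 12-site mean. The central case has intercept SD 0.188, random-slope SD 0.0314 and residual SD 0.15/√12 = 0.0433. The grid covers intercept SD 0.15-0.25, slope SD 0.020-0.0373, residual SD 0.040-0.0433, and intercept-slope correlation -0.3, 0 and +0.3.

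**3. Three-way test, central case.** For these scan times 1/Σ(t - t̄)² = 0.216, so the effective slope SD is √(0.0314² + 0.0433²×0.216) = 0.0373, matching METEOR. The SE of θ is 0.0373×√(4/126.5) = 0.0066.

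- Effects -0.029 and 0 (average -0.0145): the fitted contrast is -0.0283, slightly diluted by the two pre-randomisation scans; z = 4.27, power 98.9%.
- Effects -0.0218 and -0.0073: z is half that, power 56.8%.

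**4. Specified test, central case, effects -0.029 and 0.** With θ forced to zero, generalised least squares gives δ = a - (C_is/C_ss)·b. Here a ≈ -0.0012 and b = -0.0283 are the unconstrained intercept and slope contrasts. C_ss = 0.0373² = 0.00139, and C_is = ρ×0.188×0.0314 - 0.0433²×0.2106, where 0.2106 = 0.216×t̄ and t̄ = 0.975 years.

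| ρ | C_is/C_ss | δ (mm) | SE | Rejects |
|---|---|---|---|---|
| -0.3 | -1.56 | -0.045 | 0.032 | 29% |
| 0 | -0.28 | -0.009 | 0.034 | 6% |
| +0.3 | +0.99 | +0.027 | 0.033 | 13% |

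The true slope difference is the same in all three rows. What reaches δ is leakage through the random-effects covariance, and its sign follows ρ.

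**5. Over the grid.**

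| True slope effects | Specified test, ρ = -0.3 / 0 / +0.3 | Three-way test |
|---|---|---|
| -0.0218, -0.0073 | 9-16% / 5-6% / 6-8% | 47-83% |
| -0.029, 0 | 23-46% / 5-9% / 10-17% | 96% to over 99% |

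With a 20:80 split (-0.029 in the 20%, 0 in the 80%; central case) the figures are 6-20% against 93%. The pooled model then reports -0.0057 mm/year for both subgroups.

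**6. Checks.**

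- Simulating the central case (-0.029 and 0) with the covariance estimated by maximum likelihood gave 29.9%, 6.7% and 12.4% at ρ = -0.3, 0 and +0.3, against 98.6-98.8% for the three-way test.
- With no true subgroup difference (ρ = -0.3) the specified test rejected in 4.3%. It is not inflated; it is aimed at the wrong quantity.
- Under the Appendix C covariance, with site variation left in the residual: 25-29%, 6% and 8-12%, against 98-99%.
- A separate calculation at the 543 actually randomised, with effects -0.0145 and 0, gave 5-14% against 62-70%.

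**The case against.** The strongest reply is that the wording is shorthand. Because 4.3.1 locates the treatment effect in Time x Treatment, treatment-by-subgroup could mean the slope effect by subgroup. The promise of output like that of the primary analysis supports this, because slopes by subgroup cannot come from a model with only SUB and TRT×SUB. The authors may therefore have intended either the three-way model or separate fits. That is a fair account of possible intent, but the text names the terms to be added, and no code in Appendix C corrects it. Elsewhere the SAP does write time into an interaction when it wants one: 4.3.3 specifies a time-squared by treatment term.

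If separate fits were intended, readers would see each subgroup's slope difference and CI. The subgroups contain different subjects, so an approximate comparison could be made from two estimates and their standard errors. That point stands. The loss on this reading is smaller: no test of slope heterogeneity is prespecified, and the one that is named remains the wrong one.

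Three further points also stand. The -0.029 versus 0 scenario is extreme: twice the METEOR effect in one half and none in the other. In the milder scenario even the correct test has only 47-83% power. The sign reverses in the central case only at positive intercept-slope correlation, which the documents do not give. Finally, 4.3.7 attaches no decision rule to the subgroup results.

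**Conclusion.** The concern holds. As written, SAP 4.3.7 fixes a single slope difference across all subgroups and tests a level shift. That conclusion follows from the model terms alone.

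The size is illustrative. It rests on assumed variance components, equal subgroups (apart from the 20:80 case) and complete data. Within that range, a 0.0145 mm/year difference between subgroups would be flagged in about 5-16% of trials by the specified test, compared with 47-83% by the correct one.

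All 15 planned interaction tests are affected. The primary test of β2 and the secondary endpoints are not. This should be corrected, but it does not threaten the main conclusion of the trial.

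**What to change.** Reword SAP 4.3.7 so that each subgroup model is the primary model plus SUB, TIME×SUB, TRT×SUB and TRT×TIME×SUB. TIME×SUB is needed so that subgroups may differ in their underlying progression; without it the three-way term would absorb part of that difference. State that the interaction p-value is the test of TRT×TIME×SUB. State also that the Time x Treatment slope difference in mm/year is reported within each subgroup, by contrast from the same model, with a 95% CI. Add the matching code block to Appendix C.

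The cost is a paragraph of SAP text, one code block and two more terms in each of 15 models. It needs no new data and leaves the primary analysis unchanged.
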